10.4.4 SAFETY ANALYSES

Should an AE related to the study intervention (i.e., additional DCE-CT scans) occur, the study will be terminated. Definition and monitoring of AEs are detailed in section 8.

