8.2 CLASSIFICATION OF AN ADVERSE EVENT

8.2.1 SEVERITY OF EVENT

For AEs not included in the protocol-defined grading system, the following guidelines will be used to describe severity.

- **Mild** – Events require minimal or no treatment and do not interfere with the participant's daily activities.
- **Moderate** – Events result in a low level of inconvenience or concern with the therapeutic measures. Moderate events may cause some interference with functioning.
- **Severe** – Events interrupt a participant's usual daily activity and may require systemic drug therapy or other treatment. Severe events are usually potentially life-threatening or incapacitating.

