8.2.2 RELATIONSHIP TO STUDY INTERVENTION

Because this is an imaging study, where no clinical decision will be altered, we will only record AEs that have to do with the research procedures. The three research procedures are the pre-treatment, post-first fraction and post-treatment DCE-CT imaging.

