8.5 STUDY HALTING RULES

Administration of a study intervention will be halted when three grade 3 AEs related to DCE-CT that are determined to be at least "probably related" are reported to the clinician. The clinician will notify the study sponsor and PIs immediately when the third grade 3 event is reported and enrollment screens will stop accepting new study participants. The study sponsor will inform the UCCC DSMC members within 24 hours of this occurrence and will provide the UCCC DSMC with AE listing reports. The UCCC DSMC will convene an *ad hoc* meeting by teleconference or in writing as soon as possible. The DSMB will provide recommendations for proceeding with the study to the study sponsor. The study sponsor will inform the FDA of the temporary halt and the disposition of the study, if applicable.

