8.6 SAFETY OVERSIGHT

Monitoring and Oversight

The sponsor investigator will be responsible for monitoring the trial per the trial monitoring plan, in addition to overseeing the safety and efficacy of the trial including any specimens collected, executing the data and safety monitoring (DSM) plan, and complying with all reporting requirements to local and federal authorities. This oversight will be accomplished through additional oversight from the Data and Safety Monitoring Committee (DSMC) at the University of Colorado Cancer Center (CU Cancer Center). The DSMC is responsible for ensuring data quality and study participant safety for all clinical studies at the CU Cancer Center, which is the coordinating institution of this trial. A summary of the DSMC's activities is as follows:

- Conduct of internal audits
- Ongoing review of all serious adverse events (SAEs), unanticipated problems (UAPs) and reportable adverse events (AEs)
- Has the authority to close and/or suspend trials for safety or trial conduct issues

- May submit recommendations for corrective actions to the CU Cancer Center's Executive Committee

Per the CU Cancer Center Institutional DSM Plan, SAEs, UAPs and reportable AEs are reported to the DSMC, IRB and the sponsor investigator per protocol. All SAEs, UAPs and reportable AEs are to be reported to the DSMC within 5 business days of the sponsor investigator receiving notification of the occurrence.

Study audits conducted by the DSMC will consist of review of the regulatory records, consent forms and source data verification. Documentation of the audit conducted by the DSMC will then need to be submitted to the IRB of record at the time of the IRB's continuing review of this trial.

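### Section 10.4.4 ends the study at the first DCE-CT-related adverse event, section 8.5 only pauses it at the third grade 3 event, and nothing says which rule governs

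*Combined protocol and SAP*

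**What the plan says.** Section 10.4.4 (Safety Analyses) consists of two sentences. The first is the rule: "Should an AE related to the study intervention (i.e., additional DCE-CT scans) occur, the study will be terminated". The second is a pointer: "Definition and monitoring of AEs are detailed in section 8".

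Section 8.5 (Study Halting Rules) is the part of section 8 that deals with stopping. Its trigger reads "Administration of a study intervention will be halted when three grade 3 AEs related to DCE-CT that are determined to be at least" probably related. Screening of new participants stops at the third such event, the DSMC is told within 24 hours, and it meets ad hoc. Then "The DSMB will provide recommendations for proceeding with the study to the study sponsor", and "The study sponsor will inform the FDA of the temporary halt and the disposition of the study, if applicable". This is a reviewable pause.

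Section 8.6 separately gives the DSMC a general power: "Has the authority to close and/or suspend trials for safety or trial conduct issues". Section 5.5 lists circumstances that may justify suspension or termination and allows the study to resume once concerns are resolved. It gives no event count or grade.

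On the terms that 8.5 uses, section 8.2.1 says "For AEs not included in the protocol-defined grading system, the following guidelines will be used to describe severity" and then defines mild, moderate and severe. Section 8.2.2, which should cover relatedness, says only that "we will only record AEs that have to do with the research procedures" and names the three research scans.

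**The concern.** A stopping rule has to be unambiguous before the first event. Otherwise the choice of rule is made after the event is known. Here one mild, transient reaction to contrast requires closure under 10.4.4 and triggers nothing under 8.5. The investigator and the DSMC cannot tell from the document which applies.

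The conflict is likely to arise in practice. Under 8.1.1 and 8.2.2 the study records only events connected with the research scans, so essentially every adverse event it records, however minor, meets the 10.4.4 trigger. Section 2.3.1 names five contrast reactions, each above 1%, and describes contrast reactions as usually mild to moderate and self-limiting.

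At stake are the minimum of 10 patients that the synopsis says the aims need, and any 6-week scans still outstanding when the study closes. Those scans supply the second of the two changes from baseline in section 10.4.2.

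**Working it through.** The plan gives no operating characteristics for either rule, so there is no stated figure to reproduce. The check is mainly a comparison of text. The arithmetic only shows how differently the rules behave.

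**1. The rules side by side**

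| | Section 10.4.4 | Section 8.5 |
|---|---|---|
| Events needed | One | Three |
| Severity | Any | Grade 3 |
| Attribution | Related | At least probably related |
| Consequence | Termination, mandatory | Temporary halt |
| Review before the outcome is fixed | None | Ad hoc DSMC meeting, then advice on proceeding |

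**2. Search for a tie-breaker**

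- The pointer in 10.4.4 sends the reader to section 8 for definition and monitoring of events. It does not make termination conditional on 8.5.
- Section 5.5 is discretionary and mentions neither rule.
- Sections 8.1 to 8.4 contain no ranking. Several of their provisions presuppose a study that continues after a related event: 8.3 has non-serious reactions captured on the case report form and asks about events at each visit, and 8.4.3 allows some events to wait for continuing review.
- Section 8.6 gives the DSMC power to close or suspend, but no power to set aside the automatic termination.

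**3. Can both be obeyed?** Yes, by following 10.4.4. The study would then almost never reach a third grade 3 event, so 8.5 is essentially idle.

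**4. Illustration for 10.4.4**

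Inputs from section 2.3.1: pain 2.8%, burning 1.4%, nausea 1.2%, hot flashes 1.5%, warmth 1.1%. The documents do not say how far these overlap in the same person, so the two extremes are used:

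- full overlap: p = 2.8%
- no overlap: p = 2.8 + 1.4 + 1.2 + 1.5 + 1.1 = 8.0%

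The sample size is 10 to 15 (section 10.5), with three research scans per patient (section 8.1.1). The documents do not say whether the rates are per patient or per injection, so both are shown. The chance of at least one listed reaction in m independent units is 1 − (1 − p)^m.

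| Unit | m | p = 2.8% | p = 8.0% |
|---|---|---|---|
| Patient | 10 | 1 − 0.972^10 = 24.7% | 1 − 0.92^10 = 56.6% |
| Patient | 15 | 1 − 0.972^15 = 34.7% | 1 − 0.92^15 = 71.4% |
| Scan | 30 | 1 − 0.972^30 = 57.3% | 1 − 0.92^30 = 91.8% |
| Scan | 45 | 1 − 0.972^45 = 72.1% | 1 − 0.92^45 = 97.7% |

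**5. Illustration for 8.5**

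The documents give no grade 3 rate. Assume g between 0.1% and 2% per scan. The chance of three or more events is 1 − Σ C(m,k) g^k (1 − g)^(m−k), summed over k = 0, 1, 2.

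- 30 scans: below 0.01% at g = 0.1%; 2.2% at g = 2%
- 45 scans: below 0.01% at g = 0.1%; 6.1% at g = 2%

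Under these assumptions, 10.4.4 is likely enough to stop the study that the sponsor should plan for it, while 8.5 rarely would.

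**The case against.** The best defence is that the stricter rule is the safer one. The two can be reconciled by obeying 10.4.4, so no patient is exposed to extra risk. This is a single-site descriptive pilot with no formal hypothesis test, and no error rate is affected. Section 2.3.1 also says that no additional adverse events are expected from the scans, which might explain a zero-tolerance rule. Section 5.5 lets a stopped study resume, so closure under 10.4.4 may not be final.

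Part of this stands. The harm is loss of the study, not injury to patients. But the document nowhere says that 8.5 is meant to be idle. The expectation of no events sits beside a list of expected reactions, and a stopping rule must work when an event does occur. The resumption sentence in 5.5 does not remove a mandatory termination.

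The probabilities are also open to criticism. They count an event in any of 10 or 15 patients, whereas stopping before the tenth enrolment needs an event among the first nine: 1 − 0.972^9 = 22.6% to 1 − 0.92^9 = 52.8%, and even that counts 6-week scans that may come after the tenth enrolment. Patients with iodine contrast allergy are excluded, so the general rates may not carry over. Both points are fair, which is why the figures are illustrative only.

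Finally, severe is the third of three levels in 8.2.1, and 8.3 requires severity and relatedness to be assessed. The absence of a named scale is therefore missing detail, not part of the contradiction.

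**Conclusion.** The concern holds. Sections 10.4.4 and 8.5 give incompatible instructions for the same kind of event, and nothing in the document settles which prevails. This is an error in the text as written and must be corrected, because it concerns a rule that can end the study.

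That conclusion rests on the wording alone. The illustrative per-patient range of about 25% to 71% across 10 to 15 patients further assumes independence, every patient scanned, and every reaction attributed to the research scan. Attribution is uncertain at baseline, where the DCE-CT follows the standard-of-care simulation CT (section 7.1); this would lower the figures. Contrast nephropathy and reactions at 1% or less are not counted; including them would raise the figures, as would reading the rates per injection.

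**What to change.** Replace the termination sentence in 10.4.4 with a cross-reference to the halting rule in 8.5. Alternatively, have the sponsor and the DSMC choose one rule and state it in the same terms in both sections. Section 5.5 can stay as it is.

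If 8.5 is kept, name in 8.2.1 the severity scale that contains grade 3, and list in 8.2.2 the relatedness categories that include probably related. This is supporting detail needed to apply the rule.

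The cost is a wording amendment with IRB approval (section 13.2), and no added patients, scans or visits. The downside of keeping 8.5 is a less strict rule than 10.4.4 now sets, but the DSMC keeps its power under 8.6 to close or suspend the trial at any point.

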5.5 PREMATURE TERMINATION OR SUSPENSION OF STUDY (STUDY STOPPING RULES)

This study may be temporarily suspended or prematurely terminated if there is sufficient reasonable cause. Written notification, documenting the reason for study suspension or termination, will be provided by the suspending or terminating party to the Lead PI ([name]). If the study is prematurely terminated or suspended, the PI will promptly inform the IRB and will provide the reason(s) for the termination or suspension.

Circumstances that may warrant termination or suspension include, but are not limited to:

- Determination of unexpected, significant, or unacceptable risk to participants.
- Insufficient compliance to protocol requirements.
- Data that are not sufficiently complete and/ or evaluable.
- Determination of futility.

Study may resume once concerns about safety, protocol compliance, and data quality are addressed and satisfy the sponsor, IRB and DSMC.

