8 ASSESSMENT OF SAFETY

8.1 SPECIFICATION OF SAFETY PARAMETERS

8.1.1 DEFINITION OF ADVERSE EVENTS (AE)

Adverse event means any untoward medical occurrence associated with the use of an intervention in humans.

Because this is an imaging study, where no clinical decision will be altered, we will only record AEs that have to do with the research procedures. The three research procedures are the pre-treatment, post-first fraction, and post-treatment DCE-CT imaging.

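### Section 10.4.4 ends the study at the first scan-related adverse event of any grade, section 8.5 pauses it at the third grade 3 event, and nothing says which rule governs

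*Combined protocol and SAP*

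**What the plan says.** Section 10.4.4 (Safety Analyses) reads: "Should an AE related to the study intervention (i.e., additional DCE-CT scans) occur, the study will be terminated". It adds one cross-reference: "Definition and monitoring of AEs are detailed in section 8". Section 8.1.1 defines the term broadly: "Adverse event means any untoward medical occurrence associated with the use of an intervention in humans". Section 8.2.2 limits recording: "we will only record AEs that have to do with the research procedures".

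Section 8.5 (Study Halting Rules) has a different trigger: "Administration of a study intervention will be halted when three grade 3 AEs related to DCE-CT". It also requires that each event be judged at least probably related. At the third event, enrolment stops, the DSMC is told within 24 hours and meets ad hoc, and its recommendation goes to the sponsor. The section treats this as a pause: "The study sponsor will inform the FDA of the temporary halt and the disposition of the study, if applicable".

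Section 5.5 is a discretionary route. It lists grounds such as "Determination of unexpected, significant, or unacceptable risk to participants" and lets the study resume once concerns are resolved.

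On grading, section 8.2.1 says: "For AEs not included in the protocol-defined grading system, the following guidelines will be used to describe severity". It then gives three levels: mild, moderate and severe. On oversight, section 8.6 sends every serious adverse event (SAE) to the DSMC within 5 business days.

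On recording, section 8.3 covers events that start between consent and the last study visit. The schedule in section 7.2.7 puts the third scan at the 6-week visit and shows nothing after it. Section 5.4.2 plans no follow-up of completers.

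**The concern.** Sections 10.4.4 and 8.5 are both mandatory, and they differ in severity, count, strength of attribution and consequence. Section 10.4.4 defers to section 8 for definitions and monitoring, not for the halting rule. Section 5.5 is discretionary and does not settle the matter.

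Suppose one patient has mild nausea after an injection and it is recorded as related. Read literally, 10.4.4 ends the pilot, while under 8.5 the event does not even count towards the threshold. Section 2.3.1 expects reactions of this kind, so the case is not remote. Staff could not tell which instruction to follow, and a pilot with a minimum of 10 patients could close with little or no 6-week perfusion data.

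A lesser issue is the end of the recording window. The last contrast injection falls at what appears to be the last visit, so a delayed reaction to it may have no planned route into the data.

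**Working it through.** **Step 1. The rules side by side.**

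| | 10.4.4 | 8.5 |
|---|---|---|
| Severity | any | grade 3 |
| Count | 1 | 3 |
| Attribution | related | at least probably related |
| Consequence | termination | temporary halt, DSMC review |

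If 10.4.4 applies, the first related event closes the study, so the count in 8.5 cannot reach three in sequence. If 8.5 applies, the sentence in 10.4.4 is wrong.

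**Step 2. Can 8.5 be applied as it stands?** It counts grade 3 events. Section 8.2.1 offers only three verbal levels and mentions a grading system that the protocol does not set out. It also requires a probable relationship, but section 8.2.2, the section on relationship, lists no categories. So 8.5 needs definitions before it can serve as the single rule.

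**Step 3. How often would 10.4.4 be triggered?** The documents give no operating characteristic for either rule, so there is no planned figure to reproduce. Inputs:
- Section 2.3.1 reaction rates: pain 2.8%, burning 1.4%, nausea 1.2%, hot flashes 1.5%, warmth 1.1%.
- Section 10.5: a minimum of 10 patients.
- Section 8.1.1: three scans per patient, so 10 × 3 = 30 injections.

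Assumptions: each listed reaction is recorded as a related adverse event, every patient has all three scans, and events are independent. The documents do not say whether the rates are per patient or per injection, so both are shown.

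The chance p of any listed reaction depends on overlap. With full overlap it is the largest rate, 2.8%. With no overlap it is the sum: 2.8 + 1.4 + 1.2 + 1.5 + 1.1 = 8.0%.

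P(at least one event) = 1 − (1 − p)^n:
- Per patient, n = 10: 1 − 0.972^10 = 0.247; 1 − 0.92^10 = 0.566.
- Per injection, n = 30: 1 − 0.972^30 = 0.573; 1 − 0.92^30 = 0.918.

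The chance that 10 patients finish without triggering 10.4.4 is therefore 43 to 75% on the per-patient reading and 8 to 43% on the per-injection reading.

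**Step 4. Are these bounds?** No. Section 2.3.1 lists only reactions above 1%, and the calculation leaves out its 2% nephropathy rate. Adding that with no overlap gives p = 10%, and 1 − 0.90^10 = 0.651 or 1 − 0.90^30 = 0.958. In the other direction, the figures fall if staff do not record transient warmth or pain as adverse events, or if reactions cluster in the same patients.

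**Step 5. The 8.5 trigger.** The documents give no grade 3 rate, so its probability cannot be computed from them.

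**Step 6. Recording window.** Section 8.3 closes the window at the last study visit, so a reaction during the third-scan visit is recorded and followed. Events after the first two scans fall before a later visit. What remains is an event that starts after the patient leaves the third-scan visit.

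**The case against.** Section 10.4.4 could be read as a loose summary of 8.5. The wording does not allow it: unconditional termination on one related event does not summarise a pause after three grade 3 events.

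A better objection is that zero tolerance may be deliberate, since the scans are for research only and guide no care. The documents do not rule this out. A reader might infer that 8.5 is plainly the intended rule, but no section says so. The sponsor has to choose.

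A reader might also infer that dropping the 10.4.4 sentence leaves severe events without oversight. That goes too far. Section 8.6 already provides ongoing DSMC review of every SAE, with authority to suspend or close the study. What would be lost is the automatic stop for one or two related events that are severe but not serious.

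On recording, it is tempting to say that every reaction to the last scan is missed. The text does not support this, because the window closes at the visit and not at the injection. Section 7.2.4 also lists a final study visit, with adverse event recording and no scan, separately from the follow-up in 7.2.3 that contains the 6-week scan. It may be meant as a later visit, although 7.2.7 shows none. Section 8.3 also allows events to surface when a participant presents for care, and 8.6 states no last-visit cutoff for SAE reporting. The start-date limit in 8.3 still leaves late non-serious events uncovered.

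**Conclusion.** The contradiction between 10.4.4 and 8.5 stands, and 10.4.4 is wrong as written unless the sponsor intends zero tolerance, in which case 8.5 is wrong. The finding rests on the text alone and needs no numerical assumption. The illustrative chance that 10 patients trigger 10.4.4 is 25 to 57% per patient or 57 to 92% per injection. It depends on independence, complete scanning and each listed reaction being recorded as related. It shows that the conflict could well arise in practice, and should not be read as a forecast that the study will close.

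The recording gap is minor and conditional on 7.2.4 not being a later visit. No size is put on it, because the documents give neither a delayed-reaction rate nor an onset time. A reader might tie it to the nephropathy named in 2.3.1, but the protocol schedules no renal function test at any visit, so asymptomatic cases would go undetected after any of the three scans.

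**What to change.** 1. Keep one governing rule. Replace the termination sentence in 10.4.4 with a reference to 8.5. In 8.5, name the grading scale and define the relatedness categories, and bring 8.2.1 and 8.2.2 into line. Refer to 8.6 for the DSMC review of SAEs that already exists.

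2. If the sponsor does want zero tolerance, remove 8.5 instead and consider a severity threshold in 10.4.4, because 2.3.1 expects mild reactions.

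3. As a secondary change, extend the onset window in 8.3 for scan-related events past the final scan, with one follow-up contact, and align 5.4.2, 7.2.4 and 7.2.7. The investigators should set the length of the window. The contact would capture symptomatic delayed reactions, not asymptomatic nephropathy.

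The cost is wording changes plus one contact per patient, 10 to 15 in all. The first option is less conservative than 10.4.4 as written: one or two severe but non-serious related events would no longer stop the study automatically. Endpoints, sample size and the scan schedule do not change.

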10.4.5 ADHERENCE AND RETENTION ANALYSES

There are no pre-planned adherence and retention analyses.

10.4.6 BASELINE DESCRIPTIVE STATISTICS

Baseline descriptive statistics for patient demographics will be collected and reported.

10.4.7 PLANNED INTERIM ANALYSES

There are no planned interim analyses.

10.5 SAMPLE SIZE

The study will enroll a minimum of 10 patients with a maximum enrollment of 15 patients to allow for screen failures and dropouts. This sample size was based the number of patients that would be reasonable for the Department of Radiation Oncology to recruit within a year. The Department of Radiation Oncology treats approximately 50 liver cancer patients with SBRT per year. Assuming an enrollment rate of 40% and a dropout rate of 25%, a conservative estimate is enrolling a maximum of 15 patients in 12 months.

11 SOURCE DOCUMENTS AND ACCESS TO SOURCE DATA/DOCUMENTS

To protect confidentiality of participants, medical and research records for this trial will be maintained in compliance with regulatory and institutional requirements.

The following data will be collected on electronic-based Case Report Forms (eCRFs):

- Demographic information (age, sex, race)
- Baseline clinical information (drinking status, medications, medical treatments including cancer treatments, cancer history)
- Results of study procedures as detailed in protocol

Only the following people will have access to data and documents collected on CRFs:

- Study investigators and research staff participating in this study

Our site will permit authorized representatives of the UCCC and regulatory agencies to examine clinical records for quality assurance reviews, audits, and valuation of study safety, progress, and data validity. In addition to study monitors, study personnel on the study roster will have access to the study data.

Should study participants withdraw their consent from the study, no further data will be collected on them for this study.

Source data and documents will be kept according to HIPAA guidelines.

